Panel 3: Objectives and endpoints	29
Panel 4: Identification of investigational medicinal products	42
Panel 5: Sequence of assessments	59
Panel 6: Investigator's Global Assessment	63
Panel 7: Calculation of EASI	64
Panel 8: EASI severity score scale and area score scale	64
Panel 9: Clinical laboratory tests	71
Panel 10: Adverse events of special interest	82

List of abbreviations

AD	atopic dermatitis
ADA	anti-drug antibodies
AE	adverse event
AESI	adverse event of special interest
ALT	alanine aminotransferase
ANCOVA	analysis of covariance
anti-HCV	hepatitis C virus antibody
AST	aspartate aminotransferase
AxMP	auxiliary medicinal product
BP	blood pressure
BSA	body surface area
C _{trough}	trough concentration: lowest concentration reached by a drug before the next dose is administered
CDISC	Clinical Data Interchange Standards Consortium
CI	confidence interval
CIOMS	Council for International Organizations of Medical Sciences
CMO	contract manufacturing organisation
CONSORT	Consolidated Standards of Reporting Trials
CRA	clinical research associate
CRO	contract research organisation
C-SSRS	Columbia-Suicide Severity Rating Scale
CTR	clinical trial report
DLQI	Dermatology Life Quality Index
EASI	Eczema Area and Severity Index
EASI50	at least 50% reduction in EASI score
EASI75	at least 75% reduction in EASI score
EASI90	at least 90% reduction in EASI score
ECG	electrocardiogram
eCRF	electronic case report form
ECZTEND	tralokinumab phase 3 long-term extension trial (LP0162-1337) in subjects with AD who participated in ECZTRA trials
ECZTRA 8	ECZema TRAlokinumab trial no. 8

eDiary	electronic diary
ePRO	electronic patient-reported outcome
GCP	Good Clinical Practice
HBcAb	hepatitis B core antibody
HBsAb	hepatitis B surface antibody
HBsAg	hepatitis B surface antigen
HCP	healthcare professional
HIV	human immunodeficiency virus
HRQoL	health-related quality of life
ICH	International Council for Harmonisation of Technical Requirements for Pharmaceuticals for Human Use
ID	identification number
IEC	independent ethics committee
IGA	Investigator's Global Assessment
IGA 0/1	IGA score of 0 (clear) or 1 (almost clear)
IgE	immunoglobulin E
IgG4	immunoglobulin G4
IL-13	interleukin-13
IMP	investigational medicinal product
IRB	institutional review board
IRT	interactive response technology
IUD	intrauterine device
IUS	intrauterine hormone-releasing system
JAK	Janus kinase
JP	Japan
LOCF	last observation carried forward
MedDRA	Medical Dictionary for Regulatory Activities
NBUVB	narrow band ultraviolet B
NRS	numeric rating scale
PDE-4	phosphodiesterase-4
PEF	peak expiratory flow
PK	pharmacokinetics
PMDA	Pharmaceuticals and Medical Devices Agency

[figure not shown]
POEM	Patient-Oriented Eczema Measure
PT	(MedDRA) preferred term
PUVA	psoralen + ultraviolet A
Q2W	every second week
SAE	serious adverse event
SC	subcutaneous(ly)
SCORAD	Scoring Atopic Dermatitis
SD	standard deviation
SDTM	Standard Data Tabulation Model
SmPC	summary of product characteristics
SOC	(MedDRA) system organ class
TCI	topical calcineurin inhibitor(s)
TCS	topical corticosteroid(s)
Th2	T-helper-2
ULN	upper level of normal
UVA1	ultraviolet A1
UVB	ultraviolet B
WHO	World Health Organization

1 Protocol synopsis

Trial ID	LP0162-1343	
Title of trial	
A randomised, double-blind, placebo-controlled, phase 3 trial to evaluate the efficacy and safety of tralokinumab in combination with topical corticosteroids in Japanese subjects with moderate-to-severe atopic dermatitis who are candidates for systemic therapy.
 
ECZTRA 8 (ECZema TRALokinumab trial no. 8).
	
Short title of trial	Tralokinumab in combination with topical corticosteroids in Japanese subjects with moderate-to-severe atopic dermatitis.	
Main objectives and endpoints	
Primary objective
 
To evaluate the efficacy of tralokinumab in combination with topical corticosteroids (TCS) compared with placebo in combination with TCS in treating moderate-to-severe atopic dermatitis (AD).
 
Secondary objective (efficacy)
 
To evaluate the efficacy of tralokinumab in combination with TCS on severity and extent of AD, itch, health-related quality of life (HRQoL), and health care resource utilisation compared with placebo in combination with TCS.
	
Primary endpoints
 
 Investigator's Global Assessment (IGA) score of 0 (clear) or 1 (almost clear) (IGA 0/1) at Week 16. At least 75% reduction in Eczema Area and Severity Index (EASI75) at Week 16. 
Key secondary endpoints
 
 Change in Scoring Atopic Dermatitis (SCORAD) total score from baseline to Week 16. Change in Dermatology Life Quality Index (DLQI) score from baseline to Week 16. Reduction of Worst Daily Pruritus numeric rating scale (NRS) score (weekly average) ≥ 4 from baseline to Week 16. 
Secondary endpoints
 
 At least 90% reduction in Eczema Area and Severity Index (EASI90) at Week 16. At least 50% reduction in Eczema Area and Severity Index (EASI50) at Week 16. Percentage change in Eczema Area and Severity Index (EASI) score from baseline to Week 16. Change in Worst Daily Pruritus NRS score (weekly average) from baseline to Week 16. Change in Eczema-related Sleep NRS score (weekly average) from baseline to Week 16. Change in Patient-Oriented Eczema Measure (POEM) score from baseline to Week 16.

		
Other endpoints
 
 Reduction of DLQI score ≥ 4 points from baseline to Week 16 in subjects with baseline DLQI score ≥ 4. Reduction of POEM score ≥ 4 points from baseline to Week 16 in subjects with baseline POEM score ≥ 4. Amount of TCS (auxiliary medicinal product [AxMP]) used at Week 16. TCS (AxMP) use < 5g at Week 16. Cumulative amount of TCS (AxMP) used from baseline to Week 16.
	
Secondary objective (safety)
 
To assess the safety of tralokinumab in combination with TCS when used to treat moderate-to-severe AD for 16 weeks.
	
Secondary endpoints
 
 Number of treatment-emergent adverse events (AEs) from baseline to Week 16 per subject. Presence of treatment-emergent anti-drug antibodies (ADA) from baseline to Week 16.
Final collection of data for the primary endpoints	Week 16.	
Trial design	
This is a randomised, double-blind, placebo-controlled, parallel-group, multi-site, phase 3 clinical trial in adult Japanese subjects with moderate-to-severe AD who are candidates for systemic therapy. The trial design will support a comparison of tralokinumab in combination with TCS to placebo in combination with TCS during a treatment period of 16 weeks. A scheme of the trial design is provided below.
  
Abbreviations: AD, atopic dermatitis; TCS, topical corticosteroids; w, weeks.
	

	
The trial consists of a screening period (Week -6/-2 to Week 0), a treatment period (Week 0 to Week 16), and a safety follow-up period (Week 16 to Week 20).
 
The screening period has a minimum duration of 2 weeks and a maximum duration of 6 weeks. The exact duration of the screening period depends on the length of required washout of AD treatment as defined by the exclusion criteria. If no washout is required or if only a 2-week washout period is required, the screening period is reduced to 2 weeks and only 1 screening visit at Week -2 is required.
 
Following the screening period, eligible subjects will be randomised at baseline (Week 0) to treatment with either tralokinumab or placebo and initiate administration of the investigational medicinal product (IMP). The IMP will be administered every second week during the treatment period, and the last IMP administration (relating to this protocol) will occur at Week 14.
 
Subjects in both treatment groups will also receive an AxMP, i.e. TCS. At baseline (Week 0), the subjects will be allowed to initiate treatment once daily with the supplied TCS on areas with active lesions of AD and continue this treatment, as needed, throughout the treatment period. The TCS use will be monitored throughout the trial.
 
All subjects must use an emollient twice daily (or more, as needed) for at least 14 days prior to randomisation and will continue this background treatment throughout the trial (including the safety follow-up). On lesional skin, emollients should only be applied at a time when TCS is not applied; on TCS-untreated areas, the emollients may be applied at all times.
 
Subjects who during the treatment period or safety follow-up experience intolerable AD symptoms can be treated with rescue treatment according to investigators discretion and will thus not be deprived from effective therapy.
 
Subjects who complete the 16-week treatment period (relating to this protocol) may enter a long-term extension trial (ECZTEND). All subjects completing the treatment period, except for those who enter the long-term extension trial, will have safety follow-up assessments 6 weeks after last IMP administration.
 
The primary and secondary endpoints will be assessed at Week 16, and the final safety assessments will be conducted at Week 20.

Main assessments	
Efficacy assessments related to primary and secondary endpoints:
 
 IGA, EASI, and SCORAD (investigator assessments). DLQI, Worst Daily Pruritus NRS, Eczema-related Sleep NRS, and POEM (patient-reported assessments). 
Key safety assessments:
 
 AEs and ADA.
Main criteria for inclusion	
 Japanese subject aged 18 years and above. Diagnosis of AD as defined by the Hanifin and Rajka (1980) criteria for AD. History of AD for ≥ 1 year. A recent history (within 1 year before screening) of inadequate response to treatment with topical medication. AD involvement of $\geq 10\%$ body surface area (BSA) at screening and at baseline according to component A of SCORAD.

	
 • An EASI score of ≥ 12 at screening and ≥ 16 at baseline. • An IGA score of ≥ 3 at screening and at baseline. • A Worst Daily Pruritus NRS average score of ≥ 4 during the week prior to baseline. • Applied a stable dose of emollient twice daily (or more, as needed) for at least 14 days before randomisation.
Main criteria for exclusion	
 • Subjects for whom TCS are medically inadvisable e.g. due to important side effects or safety risks in the opinion of the investigator. • Active dermatologic conditions that may confound the diagnosis of AD or would interfere with assessment of treatment. • Use of tanning beds or phototherapy within 6 weeks prior to randomisation. • Treatment with systemic immunosuppressive/immunomodulating drugs and/or systemic corticosteroids within 4 weeks prior or randomisation. • Treatment with TCS, topical calcineurin inhibitors (TCI), topical phosphodiesterase-4 (PDE-4) inhibitors, or topical Janus kinase (JAK) inhibitors within 2 weeks prior to randomisation. • Receipt of any marketed biological therapy (i.e. immunoglobulin, anti-immunoglobulin E [anti-IgE]) including dupilumab or investigational biologic agents 3-6 months prior to randomisation. • Active skin infections within 1 week prior to randomisation. • Clinically significant infection within 4 weeks prior to randomisation. • A helminth parasitic infection within 6 months prior to the date informed consent is obtained. • Tuberculosis requiring treatment within the 12 months prior to screening. • Known primary immunodeficiency disorder.
Investigational medicinal product (IMP)	
IMP - tralokinumab
 
 • Active substance: tralokinumab. • Dosage form: solution for injection in an accessorised pre-filled syringe, 1.0 mL fill volume. • Concentration: 150 mg/mL. • Dose: 600 mg initial loading dose, then 300 mg every second week. • Method of administration: subcutaneous. 
IMP - placebo
 
 • Placebo contains the same excipients in the same concentration only lacking tralokinumab.
Auxiliary medicinal product (AxMP)	
AxMP - TCS
 
 • Active substance: mometasone furoate. • Dosage form: cream. • Concentration: 0.1%. • Method of administration: topical.
Duration of trial participation	
The trial duration for an individual subject is up to 26 weeks:
 
 • Screening period: 2 to 6 weeks.

	
 • Treatment period: 16 weeks. • Safety follow-up period: 4 weeks.
Number of subjects	Approximately 100 subjects will be randomised in a 1:1 ratio to tralokinumab+TCS or placebo+TCS.
Number and distribution of trial sites	Approximately 35 sites in Japan.
Statistical methods	
Primary endpoints The difference in response rates between treatment groups will be calculated by the Mantel-Haenszel method stratified by baseline disease severity. Subjects with missing data or subjects who receive rescue medication prior to Week 16 visit will be considered as non-responders in the analysis.
 
Key secondary endpoints The change from baseline to Week 16 in SCORAD will be analysed using an analysis of covariance (ANCOVA) model on the post-baseline responses up to Week 16. Subjects who receive rescue medication will be considered non-responders in the analysis. Missing Week 16 data among subjects who did not use rescue medication will be imputed using multiple imputation.
 
Reduction of Worst Daily Pruritus NRS weekly average of at least 4 from baseline to Week 16 is a binary endpoint, and as such it will be analysed as described for the primary endpoints.
 
Change from baseline to Week 16 in DLQI will be analysed the same way as change in SCORAD.
 
Secondary endpoints EASI90 and EASI50 are binary endpoints and will be analysed as described for the primary endpoints.
 
Percentage change from baseline to Week 16 in EASI score and change from baseline to Week 16 in Worst Daily Pruritus NRS (weekly average), Eczema-related Sleep NRS (weekly average), and POEM score will be analysed using a repeated measurements model on the post-baseline responses up to Week 16.

Signatory investigator	[name], PhD, Department of dermatology, Director, University hospital, Kyoto Prefectural University of Medicine [name].
Sponsor	LEO Pharma A/S, [name]. LEO Pharma K.K., [name] is the sponsor of the clinical trial in Japan on behalf of LEO Pharma A/S.

2 Trial identification

[figure not shown]
Trial ID: LP0162-1343

The clinical trial protocol will be registered in local registries if required by local legislation.

3 Schematic of trial design

The trial design is illustrated in [Panel 1](#).

Panel 1: Trial design

Abbreviations: AD, atopic dermatitis; TCS, topical corticosteroids; w, weeks.

4 Schedule of trial procedures

Panel 2: Schedule of trial procedures

	Screening		Treatment period										Safety follow-up ^c	Unscheduled visit, if applicable ^d	Early termination, if appl. ^e			References (protocol section)	
	Visit	Week	1 ^b	2	3	4	5	6	7	8	9	10	11		Early termination visit ^{e,f}	Nominal Week 16 visit ^{e,f}	Safety follow-up visit ^{e,f}		
Visit window (days) ^a	±3	-3	-	±3	±3	±3	±3	±3	±3	±3	±3	±3	±3	±3					
Trial population and eligibility																			
Informed consent(s) ^g	X																		8.4, Appendix 3B
Subject eligibility	X		X																8
Assessments only at screening and/or baseline																			
C-SSRS	X																		11.2.1
Demographics	X																		11.2.2
Medical/surgical history ^h	X																		11.2.3
Height and weight			X																11.2.4
BSA involvement	X		X																11.2.5
Subject assessment of efficacy																			
eDiary training/hand out		X																	11.3.4
eDiary completion ⁱ			<=====>										X		X	X			11.3.4.1-11.3.4.3
eDiary return													X		X	(X)	X		11.3.4
DLQI			X	X	X		X		X		X			X	X	X			11.3.4.4
POEM			X	X	X		X		X		X			X	X	X			11.3.4.5

	Screening		Treatment period										Safety follow-up ^c	Unscheduled visit, if applicable ^d	Early termination, if appl. ^e			References (protocol section)
	Visit	Week	1 ^b	2	3	4	5	6	7	8	9	10	11		Early termination visit ^e	Nominal Week 16 visit ^{e,f}	Safety follow-up visit ^{e,f}	
Visit window (days) ^a	±3	-3	-	±3	±3	±3	±3	±3	±3	±3	±3	±3	±3					
Investigator assessments of efficacy																		
IGA	X		X	X	X	X	X	X	X	X	X	X	X		X	X	X	11.3.1
EASI	X		X	X	X	X	X	X	X	X	X	X	X		X	X	X	11.3.2
SCORAD	X		X	X	X	X	X	X	X	X	X	X	X		X	X	X	11.3.3
Investigator assessments of safety																		
Vital signs	X		X	X	X	X	X	X	X	X	X	X	X		X	X	X	11.4.1
Physical examination	X		X											X	X	X	X	11.4.2
ECG	X		X											X	X	X	X	11.4.3
Serum pregnancy test (central laboratory)	X																	11.4.4
Hepatitis B and C, HIV (central laboratory)	X																	11.4.4
Chemistry, haematology, IgE (central laboratory)	X		X				X				X	X	X		X	X	X	11.4.4
Urine dipstick (urinalysis) ^k	X		X				X				X	X	X		X	X	X	11.4.4
Urine pregnancy test			X		X		X		X		X	X	X		X	X	X	11.4.4
ADA blood sample			X		X						X	X	X		X	X	X	11.4.4
PK blood sample					X						X	X	X		X	X	X	11.5
Adverse events	X	X	X	X	X	X	X	X	X	X	X	X	X		X	X	X	13

Visit	Screening		Treatment period									Safety follow-up ^c	Unscheduled visit, if applicable ^d	Early termination, if appl. ^e			References (protocol section)
	1 ^b	2	3	4	5	6	7	8	9	10	11	12		Early termination visit ^e	Nominal Week 16 visit ^{e,f}	Safety follow-up visit ^{e,f}	
Week	-6	-2	0	2	4	6	8	10	12	14	16	20					
Visit window (days) ^a	±3	-3	-	±3	±3	±3	±3	±3	±3	±3	±3	±3					
Other assessment																	
Photography ^l			X		X		X			X			X		X		11.7.1
Treatments and randomisation																	
Initiation of background treatment (emollients) ^m		X															9.4
Randomisation			X														9.3
IMP administration and compliance			X ^j	X ^j	X ^j	X	X	X	X	X	X		X				9.2.1, 9.8.4
TCS (AxMP) dispensing			X	X	X	X	X	X	X	X	X		X				9.2.2, 9.8.3.2
TCS (AxMP) return				X	X	X	X	X	X	X	X		X	X			9.2.2, 9.8.3.2
Concomitant medication	X	X	X	X	X	X	X	X	X	X	X	X	X	X	X	X	9.6
Concurrent procedures	X	X	X	X	X	X	X	X	X	X	X	X	X	X	X	X	9.6
Concluding forms in the eCRF^c																	
End of treatment										X				X	X		11.8
End of trial											X			X	X	X	11.8

- a) If the date of a trial visit does not conform to the clinical trial protocol, subsequent visits should be planned to maintain the visit schedule relative to randomisation/baseline (Week 0).
- b) The screening period has a maximum duration of 6 weeks, with 2 planned visits. However, for subjects who do not require washout of AD treatment or if only a 2-week washout period is required, the screening period may be reduced to 2 weeks with only 1 screening visit at Week -2 (including all assessments from both visits).

- c) An end of treatment form and end of trial form must be completed in the eCRF for all randomised subjects (Section 11.8). Subjects who complete the 16-week treatment period may enter the long-term extension trial (ECZTEND). All subjects completing the treatment period, except for those who enter the ECZTEND trial, will have final safety follow-up assessments 6 weeks after last IMP administration.
- d) Assessments to be performed at unscheduled visits will be at the discretion of the investigator.
- e) Subjects who permanently discontinue IMP or withdraw from the trial will be followed up as described in Section 10.
- f) Subjects who discontinue IMP treatment <5 weeks prior to the planned Week 16 visit will be asked to return to the trial site both at Week 16 for the nominal Week 16 visit and 6 weeks after last IMP administration for the safety follow-up visit. Subjects who discontinue IMP treatment \geq 5 weeks prior to the planned Week 16 visit will be asked to return to the trial site only at Week 16 for the nominal Week 16 visit, which also includes all planned safety follow-up assessments (Section 10.3).
- g) The informed consent form must be signed prior to performing any protocol-related procedures, including but not limited to screening evaluations and washout of disallowed medications. Screening evaluations may start at a later date than the informed consent form was signed. Additional informed consent is required for the photography component of the trial.
- h) In case medical history is incomplete at screening, missing data will be retrieved prior to randomisation.
- i) The eDiary includes: Eczema-related Sleep NRS, Worst Daily Pruritus NRS, and Patient Days of Topical Treatment Use. Subjects will complete the eDiary daily in the morning from Week -2 to Week 16, except for the Patient Days of Topical Treatment Use, which will be completed daily from Week 0 to Week 16.
- j) After the first 3 IMP administrations, all subjects will be monitored for a minimum of 30 minutes with vital signs taken at 30 minutes or until stable, whichever is later.
- k) Urine samples will be tested with a dipstick at the trial site. A urine sample will be sent to the central laboratory for further analysis only if considered required by the investigator based on the dipstick results (Section 11.4.4).
- l) At selected sites only.
- m) All subjects must use an emollient twice daily (or more, as needed) for at least 14 days before randomisation and must continue this treatment throughout the trial (including the safety follow-up period).

Abbreviations: ADA, anti-drug antibodies; appl., applicable; AxMP, auxiliary medicinal product; BSA, body surface area; C-SSRS, Columbia-Suicide Severity Rating Scale; DLQI, Dermatology Life Quality Index; EASI, Eczema Area and Severity Index; ECG, electrocardiogram; eCRF, electronic case report form; eDiary, electronic diary; HRQoL, health-related quality of life; HIV, human immunodeficiency virus; IGA, Investigator's Global Assessment; IgE, immunoglobulin E; IMP, investigational medicinal product; NRS, numeric rating scale; PK, pharmacokinetics; POEM, Patient-Oriented Eczema Measure; SCORAD, Scoring Atopic Dermatitis; TCS, topical corticosteroids.

5 Introduction and trial rationale

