In these 4 completed trials, IGA, EASI, Worst Daily Pruritus NRS, SCORAD, and DLQI were included as the main assessments supporting the multiplicity-adjusted primary and secondary efficacy endpoints. The efficacy of tralokinumab as monotherapy in subjects with moderate-to-severe AD was demonstrated in the replicate confirmatory phase 3 trials (LP0162-1325 and LP0162-1326) with statistically significant results for all primary and multiplicity-adjusted secondary endpoints at Week 16. Likewise, the efficacy of tralokinumab in combination with TCS was consistently demonstrated by statistically significant results on all primary and multiplicity-adjusted secondary endpoints at Week 16 in the LP0162-1339 trial. Non-inferiority of tralokinumab vs placebo with respect to immune responses to concomitantly administered non-live vaccines was demonstrated in the LP0162-1341 trial.

The safety evaluation of tralokinumab in AD focuses primarily on results from the 5 completed trials in AD (i.e. the AD pool). During the initial treatment period in the AD pool, the overall frequencies of AEs were similar for tralokinumab (66%) and placebo (67%). Most AEs were mild or moderate for both tralokinumab and placebo, and severe AEs occurred at a lower frequency for tralokinumab (4.6%) than for placebo (6.3%). The frequencies of AEs leading to permanent discontinuation of IMP were low and similar for tralokinumab (2.3%) and placebo (2.8%). The majority of AEs were classified as recovered/resolved for both tralokinumab (60%) and placebo (62%).

The following AEs were reported in $\geq 5\%$ of subjects in any treatment group (tralokinumab vs placebo): dermatitis atopic (15% vs 26%), viral upper respiratory tract infection (16% vs 12%), upper respiratory tract infection (5.6% vs 4.8%), and conjunctivitis (5.4% vs 1.9%).

Subgroup analyses of AEs reported in the 2 monotherapy trials (i.e. monotherapy pool) showed that the overall incidence of AEs was comparable or lower for tralokinumab every second week (Q2W) vs placebo for all the geographic regions included in these trials (Asia, Australia, Europe, and North America). Across regions, the AE profiles were overall similar to that observed for the total population, although with a tendency to lower overall incidence of AEs in North America compared with Asia, Australia, and Europe independent of treatment group.

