Panel 3: Objectives and endpoints

Objectives	Endpoints
Primary objective	
To evaluate the efficacy of tralokinumab in combination with TCS compared with placebo in combination with TCS in treating moderate-to-severe AD.	
Primary endpoints
 
 • IGA 0/1 at Week 16. • EASI75 at Week 16.
Secondary objective (efficacy)	
Key secondary endpoints
 
 • Change in SCORAD total score from baseline to Week 16. • Change in DLQI score from baseline to Week 16. • Reduction of Worst Daily Pruritus NRS score (weekly average) ≥ 4 from baseline to Week 16. 
Secondary endpoints
 
 • EASI90 at Week 16. • EASI50 at Week 16. • Percentage change in EASI score from baseline to Week 16. • Change in Worst Daily Pruritus NRS score (weekly average) from baseline to Week 16. • Change in Eczema-related Sleep NRS score (weekly average) from baseline to Week 16. • Change in POEM score from baseline to Week 16. 
Other endpoints
 
 • Reduction of DLQI score ≥ 4 points from baseline to Week 16 in subjects with baseline DLQI score ≥ 4. • Reduction of POEM score ≥ 4 points from baseline to Week 16 in subjects with baseline POEM score ≥ 4. • Amount of TCS (AxMP) used at Week 16. • TCS (AxMP) use < 5 g at Week 16. • Cumulative amount of TCS (AxMP) used from baseline to Week 16.

Objectives	Endpoints
Secondary objective (safety)	
Secondary endpoints
 
 Number of treatment-emergent AEs from baseline to Week 16 per subject. Presence of treatment-emergent ADA from baseline to Week 16.
Other objectives	
Exploratory endpoints
 
 EASI75 at each scheduled assessment. IGA 0/1 at each scheduled assessment. Change in SCORAD total score from baseline to each scheduled assessment. Change in Worst Daily Pruritus NRS score (weekly average) from baseline to each scheduled assessment. Change in DLQI score from baseline to each scheduled assessment. Reduction of Worst Daily Pruritus NRS score (weekly average) ≥ 4 from baseline to each scheduled assessment. Change in Eczema-related Sleep NRS score (weekly average) from baseline to each scheduled assessment. Change in POEM score from baseline to each scheduled assessment.

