13.6.6 Aggravation of condition

Any clinically significant aggravation/exacerbation/worsening of any medical condition(s), compared to screening, must be reported as an (S)AE in accordance with Sections [13.3](#) and [13.4](#). As AD is a fluctuating disease, consider to only report an AE if the aggravation/exacerbation exceeds normal disease fluctuation or if lesions appear in a body area which is normally not affected by AD.

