14.3.12.1 Adverse events

AEs will be coded during the course of the trial according to Medical Dictionary for Regulatory Activities (MedDRA). AEs will be presented by PT and primary system organ class (SOC).

Treatment-emergent AEs will be summarised; however, all AEs recorded during the course of the trial will be included in subject data listings. An event will be considered treatment-emergent if started after the first use of IMP or if started before the first use of IMP and worsened in severity after first dose of IMP. The tabulations described in the following will only include the treatment-emergent events. In each of the tabulations, AEs are defined by MedDRA PTs within primary SOC.

An overall summary of the number of events and the number (percentage) of subjects with any treatment-emergent AEs, deaths, SAEs, premature discontinuations from the trial due to AEs, treatment-related AEs, and severe AEs will be presented.

The number of AEs and number of subjects with each type of AEs will be tabulated by treatment group.

The severity for each type of AE will be tabulated by treatment group.

The causal relationship to IMP for each type of AE will be tabulated by treatment group. Related AEs are defined as AEs for which the investigator has not described the causal

relationship to IMP as ‘not related’. The number of related AEs and the number of subjects with each type of related AE will be tabulated.

The causal relationship to AxMP (TCS) for each type of AE will be tabulated by treatment group. Related AEs are defined as AEs for which the investigator has not described the causal relationship to AxMP (TCS) as ‘not related’. The number of related AEs and the number of subjects with each type of related AE will be tabulated.

SAEs will be evaluated separately, and a narrative will be given.

AESIs and AEs leading to withdrawal from trial or permanent discontinuation of IMP will be tabulated and listed, no narratives will be given unless the events are considered as SAEs.

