Appendix 1: Definitions of adverse events and serious adverse events

Adverse event definition

An AE is defined as any untoward medical occurrence in a patient or clinical investigation subject administered a pharmaceutical product and which does not necessarily have a causal relationship with this treatment. An AE can therefore be any unfavourable and unintended sign (including an abnormal laboratory finding), symptom, or disease temporally associated with the use of a medicinal (investigational) product, whether or not related to the medicinal (investigational) product. (35)

This definition includes:

- Accidental injuries.
- Events related to trial procedures.
- Reasons for any unfavourable and unplanned change in medication (drug and/or dose).
- Clinically significant worsening of pre-existing conditions.
- Reasons for admission to hospital or surgical procedures unless these were planned before the subject consented to trial participation.
- AEs commonly observed and AEs anticipated based on the pharmacological effect of the IMP.
- Any laboratory abnormality assessed as clinically significant by the investigator (see Section 11.4.4.2).

Serious adverse event definition

An SAE is any untoward medical occurrence that:

- Results in death.
- Is life-threatening – at risk of death at the time of the SAE (not an event that hypothetically might have caused death if more severe).
- Requires inpatient hospitalisation or prolongation of existing hospitalisation. Planned hospitalisation or planned prolonged hospitalisation do not fulfil the criteria for being an SAE but should be documented in the subject's medical record.
- Results in persistent or significant disability/incapacity.

- Is a congenital anomaly/birth defect.
- Is a medically important condition. Events that may not be immediately life-threatening or result in death or hospitalisation but may jeopardise the subject or may require intervention to prevent one of the other outcomes listed in the definition above. Examples are intensive treatment in an emergency room or at home for allergic bronchospasm, blood dyscrasias, and convulsions that do not result in hospitalisation, development of drug dependency, or drug abuse.

Definition of adverse events of special interest

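### The adverse event totals include flares of atopic dermatitis, partly an efficacy outcome; a version without that term should be prespecified beside them

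*Protocol*

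**What the plan says.** The synopsis defines the safety endpoint as a count of all treatment-emergent AEs, "Number of treatment-emergent adverse events (AEs) from baseline to Week 16 per subject", and Panel 3 (protocol Section 6) does the same as "Number of treatment-emergent AEs from baseline to Week 16 per subject". No term is excluded.

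Appendix 1 counts as an AE "Clinically significant worsening of pre-existing conditions". Section 13.6.6 repeats the rule: "Any clinically significant aggravation/exacerbation/worsening of any medical condition(s), compared to screening, must be reported as an (S)AE". For AD it adds a softer threshold: "As AD is a fluctuating disease, consider to only report an AE if the aggravation/exacerbation exceeds normal disease fluctuation", or if lesions appear where the subject does not normally have them. AD worsening above that threshold is therefore in the count.

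Section 14.3.12.1 plans "An overall summary of the number of events and the number (percentage) of subjects with any treatment-emergent AEs", with further lines for deaths, serious AEs, AE-related discontinuations from the trial, treatment-related AEs and severe AEs. The same section tabulates events and subjects by preferred term and arm, so AD worsening has its own row. SAP 6.7.1 splits the summaries by trial period and adds a search for injection site reactions. Neither document plans a total or a summary line without AD. AD worsening is not among the AEs of special interest in Panel 10.

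**The concern.** If tralokinumab works, it reduces flares. Each reported flare avoided lowers the tralokinumab AE count for a reason unrelated to how well the drug is tolerated. A total that mixes this benefit with the harms lets the two partly cancel. A finding that overall AE frequency is close to placebo could then reflect fewer flares, a lack of other harms, or some of each, and the total alone does not say which.

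The sponsor's own pool gives reason to look. AD worsening was clearly less frequent on tralokinumab, the other three AEs reported at 5% or more were all more frequent, and the overall frequencies were almost equal. With about 50 subjects per arm and no formal testing (protocol 14.3.5), the safety reading of this trial rests on descriptive totals, so what they contain matters.

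**Working it through.** The documents give no expected AE rate, power or precision for this endpoint, so there is no planned figure to reproduce. All rates below are percentages of subjects in the AD pool (protocol 5.2).

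| Term | Tralokinumab | Placebo | Difference (points) |
|---|---|---|---|
| Any AE | 66 | 67 | −1 |
| Dermatitis atopic | 15 | 26 | −11 |
| Viral upper respiratory tract infection | 16 | 12 | +4.0 |
| Upper respiratory tract infection | 5.6 | 4.8 | +0.8 |
| Conjunctivitis | 5.4 | 1.9 | +3.5 |

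**1. Direction.** The three non-AD terms sum to 4.0 + 0.8 + 3.5 = +8.3 points, against −11 for AD. This shows that the offset can happen. It covers only terms at 5% or more and adds subject percentages, so it does not give the sign of the whole.

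**2. Size at 50 per arm.** Subjects with an AD AE: 50 × 0.15 = 7.5 and 50 × 0.26 = 13, a difference of 5.5. With one event per affected subject this is 5.5/50 = 0.11 AEs per subject. If events were Poisson, the rates −ln(1 − p) are 0.163 and 0.301, and 50 × 0.139 = 6.9 events. Assumed smaller gaps, to allow for topical corticosteroid in both arms: 18% vs 10% gives 50 × 0.08 = 4.0 subjects, and 10% vs 5% gives 50 × 0.05 = 2.5. If placebo has 1 to 3 AEs per subject (assumption; the documents give none), 0.11 is 0.11/(3 − 0.26) = 4% to 0.11/(1 − 0.26) = 15% of its non-AD count.

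**3. Subjects with any non-AD AE.** Let f be the share of subjects with an AD AE who have no other AE. The documents do not give f. In each arm the non-AD rate is the any-AE rate minus f times the AD rate. With the same f in both arms, the difference is (66 − 15f) − (67 − 26f) = −1 + 11f points.

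| f | Tralokinumab | Placebo | Difference (points) |
|---|---|---|---|
| 0 | 66.0 | 67.0 | −1.0 |
| 0.5 | 58.5 | 54.0 | +4.5 |
| 1 | 51.0 | 41.0 | +10.0 |

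The difference is zero at f = 1/11 = 0.09. If AD and non-AD AEs were independent, the rates would be 1 − 0.34/0.85 = 60.0% and 1 − 0.33/0.74 = 55.4%, or +4.6 points. If f may differ by arm, the limits are 51 − 67 = −16 and 66 − 41 = +25 points.

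**4. What the planned tables recover.** Events add up, so total events minus the AD row, divided by the number of subjects, gives the mean non-AD count exactly. Subjects do not add up, because one person can have several AEs. Preferred-term rows therefore cannot return the number of subjects with any non-AD AE, or with any severe, related or discontinuation-causing one.

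**The case against.** The strongest reply is that nothing is concealed. AD has its own row by arm, severity and causality are tabulated by type, AEs leading to discontinuation are tabulated and listed, and all AEs go into subject listings. The named endpoint is an event count, and its mean without AD follows by subtraction. That stands: a reader might infer that the plan hides other harms, and the documents do not support this. In the earlier trials the sponsor stated openly in protocol 5.2 that conjunctivitis, keratitis and injection site reactions were more frequent on tralokinumab. What remains is the subject-level lines, which would have to be rebuilt by hand from listings, under a rule chosen after unblinding.

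The size is also open to challenge. The pool includes two monotherapy trials, and the range for f leaves even the direction of the non-AD difference open. The shift is small against the noise: with an assumed 0.8 to 1.8 AEs per subject, the Poisson standard error of the difference is √(2 × 0.8/50) = 0.18 to √(2 × 1.8/50) = 0.27, so 0.11 is about 0.4 to 0.6 standard errors. All of that stands. It limits what can be claimed about magnitude, but the shift is systematic: it has the same direction whenever the drug reduces reported flares.

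Finally, AD worsening is a legitimate AE, and removing one term while keeping other disease-linked ones, such as eczema herpeticum, is a choice. This argues against replacing the total. It does not argue against a second version beside it.

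**Conclusion.** The point holds as a limited one. The AE count per subject and the overall summary mix a partly efficacy-driven term with the other AEs, and can partly offset an excess of those others. At pooled rates the offset is about 5.5 subjects with 50 per arm, or 2.5 to 4.0 under the smaller assumed gaps. For subjects with any non-AD AE, the pool implies −1 + 11f points with f unknown and taken as equal in both arms.

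Three stronger readings go beyond the documents. One is that the pool shows a reversed sign once AD is removed: the four-term sum leaves out every rarer AE, and +4.6 points needs independence. Another is that the severe, related and discontinuation lines are distorted: the documents give no AD share for any of them, so it can be said only that they cannot be separated from the preferred-term tables. The third is that the statement on harm should rest on the version without AD alone: that would take genuine AEs out of the headline, and is a trade-off rather than a correction.

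**What to change.** In protocol 14.3.12.1 and SAP 6.7.1, keep the all-AE totals unchanged. Beside them, prespecify by arm the treatment-emergent AEs per subject to Week 16, and each line of the overall AE summary, excluding preferred term *Dermatitis atopic*. Show that term on its own line, and state that the two versions will be interpreted together. Fix the rule before the randomisation code is broken.

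No new data are needed. The protocol already uses this preferred term, for the indication, in its rescue algorithm (14.3.4), and SAP 6.7.1 already runs a term-based AE search. The cost is one more table, and a headline comparison that may look less favourable to tralokinumab.
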